7.7 Data Sources

This is an observational study that will use nationwide data from various registries and databases in Sweden, Denmark, and Norway to monitor incidence rates of upper airway

PRODUCT: V501/V503	PROTOCOL/AMENDMENT VERSION NO.: V503-088-01-v1
REVOPS ID NO: NIS009722	CORE DRC APPROVAL DATE: 18JUL2024
EPIDEMIOLOGY NO.(PE STUDIES ONLY): EP08039.017	

HPV-related diseases over time. The diseases of interest are collected prospectively on a routine basis and recorded in the registries, thereby allowing the opportunity to conduct retrospective studies.

All registry data can be linked by a unique personal identification number (PIN) that is assigned to each resident at birth (or at the time of immigration into the countries) and does not change through the resident's lifetime. Therefore, the existing infrastructure and registry systems in Nordic countries are an excellent resource for monitoring the burden of HPV-related disease in the general population. The registries in Nordic countries are accurate, complete, and have high population coverage, thereby minimizing some biases inherent in observational studies, such as selection of the study population, recall bias, and lack of access to complete medical records [36] [37] [38].

The study will be conducted using only structured secondary data. The data sources for this study include population, cancer, and vaccine registries. Examples of the data that may be available from these types of registries are shown below for each participating country.

Data sources for this study include for **Sweden** the following population, patient, and vaccine registries:

Total Population Registry

- date of birth
- gender
- migration status
- date of death, if applicable

National Patient Registry

- diagnosis of RRP (both JoRRP and AoRRP)
- diagnosis of external genital warts (own and maternal)
- treatment codes DQB10 (Endoscopic extirpation), UDQ25 (Microlaryngoscopy with biopsy), UDQ22 (Microlaryngoscopy)

PRODUCT: V501/V503	PROTOCOL/AMENDMENT VERSION NO.: V503-088-01-v1
REVOPS ID NO: NIS009722	CORE DRC APPROVAL DATE: 18JUL2024
EPIDEMIOLOGY NO.(PE STUDIES ONLY): EP08039.017	

Prescribed Drug Registry (PDR)

- ATC code (HPV vaccine: J07BM01 [GARDASIL-4] and J07BM03 [GARDASIL-9], genital warts treatment: D06BB10 and D06BB04)
- date(s) of administration
- other types of information from PDR relevant to understand dosing pattern of relevant products

National Vaccination Registry and Swedish Vaccination Registry (SVEVAC)

- type of vaccine received
- brand name
- date(s) of administration

Multigenerational registry

• index data for linking to mothers of cases and controls in the primary objective to obtain maternal history of EGW

LISA database

- education level of the subject
- parental education level
- individual and household income

Data sources for this study include for **Denmark** the following population, patient, and vaccine registries:

Population Registry (Danish Civil Registration System) (includes information on all residents in Denmark and is daily updated with information on emigration, immigration, death)

- date of birth
- gender
- migration status
- date of death, if applicable

National Patient Registry (contains information on all diagnoses and treatment/procedures related to admissions to hospitals (since 1978) and outpatient clinics (since 1995)

- diagnosis of RRP (both JoRRP and AoRRP)
- date(s) of RRP diagnosis
- procedure and treatment codes in relation to RRP
- diagnoses of genital warts (GWs)

PRODUCT: V501/V503	PROTOCOL/AMENDMENT VERSION NO.: V503-088-01-v1
REVOPS ID NO: NIS009722	CORE DRC APPROVAL DATE: 18JUL2024
EPIDEMIOLOGY NO.(PE STUDIES ONLY): EP08039.017	

• date(s) of GWs

National Health Service Registry (contains information on all HPV vaccination given free of charge

- type of HPV vaccine received
- number of doses
- dates of administration

National Prescription Register (contains information on all redeemed prescription in Denmark since 1995 - including HPV vaccines bought at own cost)

- type of HPV vaccine received
- number of doses
- dates of administration
- prescription of Podophyllotoxin (drug of choice in Denmark for treatment of GWs)
- dates of administration

Statistics Denmark

- educational level
- income

Pathology Register

- Topography/SNOMED codes in relation to RRP
- Date(s) of RRP diagnosis

Data sources for this study include for **Norway** the following population, patient, and vaccine registries:

National population registry

- Date of birth
- Gender
- Migration, if applicable
- Date of death, if applicable
- Index data for linking to mothers of cases and controls in the primary objective, e.g., to obtain maternal history of vaccination.

PRODUCT: V501/V503	PROTOCOL/AMENDMENT VERSION NO.: V503-088-01-v1
REVOPS ID NO: NIS009722	CORE DRC APPROVAL DATE: 18JUL2024
EPIDEMIOLOGY NO.(PE STUDIES ONLY): EP08039.017	

Norwegian patient registry

- Diagnosis, including date, of RRP
- Treatment codes, including dates, DQB10 (Endoscopic extirpation), UDQ25 (Microlaryngoscopy with biopsy), UDQ22 (Microlaryngoscopy)
- Diagnosis, including date, of AGW (own and maternal)

Norwegian cancer registry

Norpat codes on morphology/topography to increase specificity of RRP diagnosis (if feasible)

Norwegian Prescribed Drug Registry

- ATC code (HPV vaccine: J07BM01 Gardasil-4, J07BM02 Cervarix, J07BM03 Gardasil-9), genital warts treatment: D06BB10 Imiquimod and D06BB04 Podophyllotoxin, chlamydia treatment: J01AA02 Doxycycline
- Date(s) of administration
- Other types of information relevant to understand dosing pattern of relevant products

Norwegian Immunisation Registry (SYSVAK)

- Type of HPV vaccine (Gardasil/Gardasil9/Cervarix)
- Date(s) of administration

Statistics Norway

- Education level (subject/parents)
- Annual individual and family income

7.7.1 Study Procedures

The proposed study is non-interventional in nature and does not entail any risk to the study participant, apart from the possibility of integrity breach through accessing public records. Therefore, it must be subject to approval from the ethics review committees in each of the respective countries to mandate this access. All study investigators/research institutions have substantial experience in handling similar studies in an integrity-assured manner and numerous safeguards are in place to maintain confidentiality of information on the study subjects. Also, all data are pseudonymized and the researcher does not have access to the underlying identifiers as these are protected separately by the data holder authority.

PRODUCT: V501/V503	PROTOCOL/AMENDMENT VERSION NO.: V503-088-01-v1
REVOPS ID NO: NIS009722	CORE DRC APPROVAL DATE: 18JUL2024
EPIDEMIOLOGY NO.(PE STUDIES ONLY): EP08039.017	

7.8 Study Size

Power analysis for the primary objective (nested case-control study):

Estimated power to evaluate the primary objective is presented in this section. Our primary hypothesis is that AoRRP risk is lower among females fully vaccinated with Gardasil before age 17 years versus those who are never vaccinated before case/control selection. This could be also stated as AoRRP risk is higher among females unvaccinated for HPV compared to those who are vaccinated at age < 17 years. The statistical criterion for success requires that the odds ratio (OR) for this comparison be \geq 3.0 and lower bound of the 95% confidence interval (CI) for the OR be \geq 1.33. In observational studies, high effect estimates are considered important to demonstrate strong associations and to assess causality. Conventionally, odds ratios of <2 are considered to represent weaker associations by epidemiologists, as it may not be possible to judge whether the association can be entirely accounted for by bias [39]. A threshold of 3.0 is therefore proposed to establish the effectiveness of Gardasil vaccination in preventing RRP. Prior Nordic registry studies reported Gardasil effectiveness against genital warts ranging from 38%-88% (equivalent to ORs of 1.6-8.3) and cervical intraepithelial neoplasia grade 2+ ranging from 22%-82% (equivalent to ORs of 1.3-4.0) with higher effect among females vaccinated at younger age.

Based on prior available information (i.e., publicly available gross statistics on ICD codes for otorhinolaryngological diseases), the Sponsor's power calculations (summarized below) at first suggested that it may be possible to test this hypothesis in Sweden alone. However, at the time when this protocol was initially drafted, the exact number of cases were not known and therefore it was noted that a decision to conduct the analysis would be made once data were received from the registries, i.e., when the exact number of cases occurring in relevant birth cohorts was confirmed.

Estimated number of AoRRP cases:

The number of possible AoRRP cases (identified using ICD-10 code D14.1) occurring after Gardasil introduction in Sweden, Denmark, and Norway (among females eligible for vaccination before 17 years of age) were estimated by accessing publicly available gross statistics on ICD-10 codes for otorhinolaryngological diseases, and without assessing the proportion of vaccinated individuals among cases and controls, or conducting any preliminary analyses evaluating the association between HPV vaccination and RRP. Initial case counts from Sweden were expected to be between 30 and 60; recent assessment of the total number of cases in the birth cohorts of interest were 46. In Denmark, the estimated number of possible AoRRP cases (identified using ICD-10 code D14.1) occurring after Gardasil introduction was estimated to be between 50 to 90 in eligible birth cohorts. After applying appropriate topography and SNOMED codes to improve specificity, the number of AoRRP cases will be < 50. In Norway, the estimated number of possible AoRRP cases identified in the Norwegian Patient Registry among females ages 15-29 years for the calendar years 2006-2020 (using ICD-10 code D14.1) and birth cohorts of interest (1990+) is between 40 to 70 cases. These numbers will likely be lower after using appropriate topography/morphology (Norpat) codes to improve specificity (also <50).

PRODUCT: V501/V503	PROTOCOL/AMENDMENT VERSION NO.: V503-088-01-v1
REVOPS ID NO: NIS009722	CORE DRC APPROVAL DATE: 18JUL2024
EPIDEMIOLOGY NO.(PE STUDIES ONLY): EP08039.017	

Power calculations:

Study power was estimated according to varying number of AoRRP cases (from 40 to 80), effect size (odds ratio from 3.0 to 4.0), and weighted female vaccination coverage (20 to 30%) with constant alpha-level of 0.05, control/case ratio of 10 in the age range of focus (Table 1). To detect a true OR of 3.0 with an overall vaccination coverage of 25% in all three countries combined, approximately 60 AoRRP cases would be needed to achieve a power of at least 80%, which would not be possible by including data from individual countries alone. Precision was also considered by specifying that the analyses for the primary objective be powered to detect an OR of at least 3.0, with a lower bound for the confidence interval of at least 1.33, which is equivalent to lower bound of 95% CI of vaccine effectiveness >25%. Preliminary estimates of vaccination coverage among females in the proposed age group (<17 years) obtained from public registries are ~20% for Sweden, ~50% for Denmark, and ~25% for Norway, and is expected to be at least 25% overall. By pooling data from Sweden, Denmark, and Norway for the primary analysis, the estimated combined number of AoRRP cases occurring after Gardasil introduction in these three countries (birth cohorts 1990+) is expected to be above 60 with >80% power assuming true odds ratio of 3.0 and 25% vaccination coverage (Table 2). Previously, individual level registry data were successfully pooled across multiple Nordic countries (Denmark, Finland, and Sweden) in a case-control study evaluating risk of male breast cancer in association with finasteride use [40].

In Sweden, Denmark and Norway, the attribution of HPV types contributing to HPV-related diseases (including RRP) is similar, and the median age of sexual debut among females is also similar (~16 years) [28]. As expected, prior studies in these countries have reported similar vaccine effectiveness against HPV-related diseases, including against cervical cancer in Sweden and Denmark, i.e., 88% and 86% effectiveness among females who were vaccinated at <17 years of age, respectively [20] [21]. Also, in a very recent Norwegian analysis focusing on Gardasil vaccine effectiveness against CIN2+, investigators reported 82% effectiveness among females vaccinated <17 years of age (lower compared with estimates above but expected given the higher attribution of HPV types other than 16 and 18 in cervical precancer versus cancer) [41].

PRODUCT: V501/V503	PROTOCOL/AMENDMENT VERSION NO.: V503-088-01-v1
REVOPS ID NO: NIS009722	CORE DRC APPROVAL DATE: 18JUL2024
EPIDEMIOLOGY NO.(PE STUDIES ONLY): EP08039.017	

Table 2 Power estimates according to varying number of cases of AoRRP (from 40 to 80), effect size (odds ratio from 3.0 to 4.0), and vaccination coverage (20-30%), with constant alpha-level of 0.05, lower bound of 95% confidence interval >1.33, control/case ratio of 10.

True	%	Number of AoRRP cases								
effect size	Vaccine coverage	40	45	50	55	60	65	70	75	80
OR = 3	20	0.40	0.46	0.48	0.52	0.57	0.60	0.61	0.65	0.68
	25	0.67	0.71	0.76	0.76	0.80	0.82	0.82	0.85	0.87
	30	0.85	0.87	0.88	0.91	0.92	0.93	0.94	0.95	0.96
OR = 3.5	20	0.48	0.55	0.60	0.65	0.68	0.71	0.75	0.75	0.80
	25	0.77	0.79	0.83	0.86	0.87	0.90	0.92	0.93	0.93
	30	0.91	0.93	0.94	0.95	0.96	0.97	0.98	0.98	0.98
OR = 4	20	0.57	0.63	0.68	0.74	0.76	0.79	0.83	0.85	0.87
	25	0.84	0.86	0.89	0.92	0.93	0.94	0.95	0.96	0.97
	30	0.95	0.96	0.97	0.98	0.98	0.99	0.99	0.99	0.99

Regarding evaluation of Gardasil effectiveness against JoRRP, the Sponsor has similarly proposed including additional data from Denmark and Norway due to study power limitations in Sweden alone.

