Controls: For each case of AoRRP, 10 control subjects free of this diagnosis, at the time of the case's diagnosis, will be identified from the respective countries where cases were diagnosed. As the number of controls per case increases beyond 4, improvement in statistical power diminishes [30]. However, given that data for additional controls are readily available in this database study, 10 controls per case will be selected. Cases and controls will be matched on age (+/- 1 year) at diagnosis, calendar year, and the region where case was diagnosed. By design of the study (nested case-control), cases and controls will also be matched according to length of follow-up in the registries. Controls will be selected from the population at risk at the point in time when a case is diagnosed with RRP. All controls who met the matching criteria will be assigned a random number using SAS statistical software (SAS Institute Inc, Cary, NC) procedures. Then, 10 controls for each case will be selected at random from the pool of eligible controls. Controls will be assigned the same index date as the case to which they are matched. Figure 2 provides an example of case/control subject selection nested within population-based cohort (2006-2021) in this study.

PRODUCT: V501/V503	PROTOCOL/AMENDMENT VERSION NO.: V503-088-01-v1
REVOPS ID NO: NIS009722	CORE DRC APPROVAL DATE: 18JUL2024
EPIDEMIOLOGY NO.(PE STUDIES ONLY): EP08039.017	

Figure 2 Example of case/control subject selection nested within population-based cohort (2006-2021) in this study. Subject 1 is classified as a case without exposure to Gardasil prior to the index (diagnosis) date, and subject 2 is an eligible matched control with exposure to Gardasil prior to the index date.

Exposure assessment: The exposure of interest is GARDASIL or GARDASIL 9 vaccination prior to the index date for each case and matched controls. GARDASIL is a quadrivalent vaccine that is effective against HPV types 6/11/16/18, while GARDASIL 9 is a nonavalent vaccine that is effective against HPV types 6/11/16/18/31/33/45/52/58.

Exposure will be defined in 2 ways:

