12 ANNEXES

Annex 1 Graphical And Numerical Overview Of Potential Confounding In Assessment Of Hpv Vaccine Effectiveness Against Adult-Onset Rrp

Definitions:

Study exposure: HPV vaccination with GARDASIL or GARDASIL 9, below called HPV vaccination.

Study outcome: Adult-onset recurrent respiratory papillomatosis, below called RRP.

Primary objective: Estimate odds ratio (OR) of RRP (yes/no) given HPV vaccination (yes/no).

Power: The study has $\ge 80\%$ power to detect an OR of 3.0 with a lower bound of the 95% confidence interval of ≥ 1.33 , assuming at least 60 cases of AoRRP are observed.

Main association of interest:

The hypothesis is that HPV vaccination is negatively associated with the odds (likelihood) of RRP. Factors that may act as confounders to this association are considered, below. That is, factors associated with both exposure and outcome in such a way that an observed association between the two is partially or completely confounded.

Potential confounders:

Factors that are established to be associated with exposure/HPV vaccination in Nordic countries (Sweden, Denmark, and Norway):

1) Socioeconomic status:

In studies evaluating factors associated with uptake of HPV vaccination in the Nordic region, low education and low-income level of parent(s) were found to be associated with lower vaccine uptake [44][35]. Statistically significant associations (95% CIs excluded null) were observed when focusing on girls in the free of charge school-based program (hazard ratio [HR] or odds ratio [OR] estimates ranging from: 0.75 to 0.92 for low education and from 0.67 to 0.87 for low income in Denmark and Sweden, respectively) and the subsidized program in Sweden (HR=0.53 for low income and HR=0.32 for low education). Additionally, in Denmark, investigators assessed association between vaccine uptake and country of birth and found that uptake was significantly lower if born outside of Denmark (OR=0.49, 95% CI=0.42-0.57) [44]. Similarly, in Sweden, investigators assessed association between vaccine uptake and country of birth and found that uptake was significantly lower if born outside of Sweden (OR=0.49, 95% CI=0.48-0.50) [35].

PRODUCT: V501/V503	PROTOCOL/AMENDMENT VERSION NO.: V503-088-01-v1
REVOPS ID NO: NIS009722	CORE DRC APPROVAL DATE: 18JUL2024
EPIDEMIOLOGY NO.(PE STUDIES ONLY): EP08039.017	

2) Sexual behavior:

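### Table 2's 80% power with 60 cases does not reproduce under its stated criterion (lower 95% limit above 1.33): it is about 45 to 55%, and 0.80 matches excluding OR = 1

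*Protocol*

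**What the plan says.** Section 7.8 (Power calculations) takes a true OR of 3.0 and a pooled coverage of 25%, and says that "approximately 60 AoRRP cases would be needed to achieve a power of at least 80" percent. The next sentence says that the primary analysis is to be powered for an OR of at least 3.0 with a lower confidence limit of at least 1.33, and the one after it puts overall coverage at 25% or more.

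The caption of Table 2 gives the conditions for its 81 cells, ending with "lower bound of 95% confidence interval >1.33, control/case ratio of 10". The cell for OR 3, 25% coverage and 60 cases is 0.80.

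Section 2 (Abstract, Data Analysis) links about 80% power at 60 cases to a lower limit of 1.33. Annex 1 (Power) claims 80% or more with a lower limit of 1.33 or more, "assuming at least 60 cases of AoRRP are observed".

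The success rule in Sections 2 and 7.8 has two parts: an estimated OR (unvaccinated versus vaccinated) of 3.0 or more, and a lower 95% limit of 1.33 or more. Section 7.11 specifies conditional logistic regression but not the type of interval. No power formula or software is named.

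**The concern.** Power for a lower limit above 1.33 must be lower than power for a lower limit above 1. With 60 cases and 25% coverage, only about 6 vaccinated cases are expected at OR 3, so the interval is wide and 80% against 1.33 looks too high. The change with coverage at OR 3 and 60 cases (0.57, 0.80, 0.92 for 20, 25 and 30%) also looks too steep.

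Section 7.8 uses the table to argue that a pooled study with more than 60 cases has over 80% power. If the true figure is near one half, a pooled study of about that size that misses 1.33 could be read as evidence against effectiveness when it is mostly low power.

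**Working it through.** **Inputs (Section 7.8, Table 2, Section 7.1).** 60 cases; 10 controls per case, so 600 controls; coverage 25%, taken as that among controls; true OR 3.0; two-sided 95% limits, since the criterion is a 95% confidence limit.

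**Expected counts.** Vaccinated share among cases = (0.25/3) / (0.75 + 0.25/3) = 0.10. Cases: 6 vaccinated, 54 unvaccinated. Controls: 150 and 450.

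**Wald formula.**
- SE(log OR) = sqrt(1/6 + 1/54 + 1/150 + 1/450) = 0.4405.
- Lower limit at an estimate of exactly 3.0: 3.0 × exp(−1.96 × 0.4405) = 1.27, below 1.33.
- Power for a limit above 1.33: Φ((ln 3 − ln 1.33)/0.4405 − 1.96) = Φ(−0.11) = 0.455.

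**Checks.** Exact binomial enumeration of the Wald limit gives 0.45 to 0.46. Simulated 1:10 conditional logistic regression gives about 0.45 (Wald), 0.48 (score) and 0.54 to 0.55 (likelihood ratio).

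**Trying to reproduce 0.80.** With threshold 1, exact enumeration gives 0.800 and simulation 0.799. The two-sided Wald formula gives Φ(1.098612/0.4405 − 1.96) = 0.70, because it ignores the skewness that comes with about 6 vaccinated cases. Its one-sided 5% version gives 0.802. So 0.80 is reached against OR = 1 and not against 1.33.

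**Other cells (exact enumeration, two-sided Wald limit).**

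| OR | Coverage | Cases | Table 2 | P(limit ≥ 1.33) | P(limit > 1) |
|---|---|---|---|---|---|
| 3 | 20% | 60 | 0.57 | 0.332 | 0.678 |
| 3 | 25% | 60 | 0.80 | 0.456 | 0.800 |
| 3 | 30% | 60 | 0.92 | 0.555 | 0.874 |
| 3 | 30% | 40 | 0.85 | 0.350 | 0.682 |
| 4 | 25% | 60 | 0.93 | 0.690 | 0.929 |

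Against 1.33, none of the 81 cells agrees within 2 points; all are overstated, by 8 to 50 points. Against 1, some agree (26 to 29 of 81, depending on details of the enumeration) and the rest do not. One-sided limits, other variance forms, other readings of coverage and other control ratios matched no more than 29 cells.

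**Cases needed for 80% on the lower bound alone (OR 3, 25%).**
- Wald formula: required SE = (ln 3 − ln 1.33)/(1.96 + 0.8416) = 0.2903. SE² scales as 1/n, so n = 60 × 0.19407/0.08430 = 138.1, that is 138 to 139.
- Exact enumeration and simulation, Wald limit: about 116 to 117.
- Likelihood-ratio limit: about 107.

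**Full success rule.** At a true OR of 3.0, the estimate reaches 3.0 about half the time whatever the sample size, and this caps the joint probability. Computed values are 0.51 to 0.52 at 107 to 138 cases. At 60 cases with a Wald limit, the lower bound is the tighter condition and the joint probability is about 0.45.

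**The case against.** **The main sentence can be read without the 1.33 bound.** It speaks of detecting an OR of 3.0 at alpha 0.05, and for excluding OR = 1 the 80% is right. This stands for that sentence alone. It does not cover the caption of Table 2, the abstract or Annex 1, which attach 1.33 to the figure. The abstract might mean the limit that accompanies an observed OR of 3.0; on the expected counts that limit is 1.27 (Wald) to 1.37 (profile likelihood), but it describes precision and is not a power.

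**A reader might infer that power must be below 50%.** That holds only for Wald limits. The protocol does not fix the interval, and a likelihood-ratio limit gives up to about 55%.

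**A reader might infer that the study is underpowered or that pooling was misjudged.** The documents do not support this. Sixty is neither a recruitment target nor a stopping point: all registry cases enter, and the total is expected to exceed 60. Section 7.8 gives 46 cases in Sweden and fewer than 50 in each other country, so at most 46 + 49 + 49 = 144. It also gives coverage of about 20, 50 and 25%. Under an assumed split of 46/30/30 cases with those coverages, the lower-bound condition is met with simulated probability 0.82. An equal mix of those coverages at 60 cases gives about 58%. Lower power in one country is a reason for pooling.

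**A reader might infer that the authors simply left out the 1.33 bound throughout.** No method is named, and many cells do not fit threshold 1 either. The cause is unknown.

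**Conclusion.** The point holds. Under the criterion printed with Table 2, power at OR 3.0, 25% coverage and 60 cases is about 45% (Wald) to 55% (likelihood ratio), some 25 to 35 points below the stated 80%. The stated figure equals the power to exclude OR = 1, and much of the table fits neither threshold.

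Eighty percent on the lower-bound condition alone needs about 107 to 139 cases, which is in the upper part of the possible range but within it. It would be wrong to conclude that this many cases gives 80% power for study success: the OR ≥ 3.0 condition keeps that near 50% at a true OR of 3.0.

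These figures assume that 25% is the coverage among controls, and that no information is lost to covariate adjustment or to partly vaccinated women. A country mix averaging 25% leaves the Wald result at about 45%.

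**What to change.** Recompute every cell of Table 2 under 1:10 conditional logistic regression, and name the method, the interval type and the threshold. Report two probabilities: that the lower 95% limit is at least 1.33, and that the full success rule is met. Replace the claim that 60 cases give 80% in Section 2, Section 7.8 and Annex 1 with the recomputed figures.

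If 80% is meant as the power to exclude OR = 1, say so and remove the 1.33 label from it. Relabelling alone is not enough: at OR 3 and 60 cases, the 20% and 30% coverage cells would then be about 0.68 and 0.87, not 0.57 and 0.92, so the table must still be recomputed.

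The cost is one simulation and corrected text. The stated power becomes less favourable. No change to the design is needed.
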